Analyses for Aim 1 will include a descriptive examination of household COVID testing uptake and previous COVID testing utilizing the COVID-19 Symptoms, Diagnoses, and Testing Scale for participants at baseline. This scale includes variables such as symptoms, whether participant has ever been tested for COVID, and COVID test results. These data are dichotomous and nominal in nature. To address Aim 1, the following analyses will be conducted. Data will be stratified with respect to important demographic factors (e.g., age, race, gender, ethnicity, essential worker). Nominal variables (i.e. COVID-19 symptoms, test frequency) will be summarized using frequencies and percentages. Bivariate analyses will be conducted to examine associations between testing practices and key predictors (intervention group), confounders (i.e. previous infection or vaccination), moderators (i.e. essential worker status, testing fatigue), and demographic characteristics (e.g., age, gender, race, ethnicity). A two-sample test for proportions will be used to compare the baseline testing practices of the two treatment groups. Chi-square tests will be used to assess group differences for nominal data. The Fisher's exact test will be considered for contingency tables with sparse cells. We will compare outcomes across 3 racial/ethnic groups (White, Black, Hispanic). These differences will be examined in bivariate analyses (unadjusted) and multivariable analysis (adjusted). We will develop multilevel multivariable regression models to examine the association between the key predictors, mediators, and moderators, such as vaccination, testing fatigue, or exposure, on baseline testing uptake.

Aim 2 is to explore acceptability, facilitators and barriers to testing, social distancing, wearing face masks, naming contacts, isolation or quarantine, and accessing COVID-19 related health services.

Analysis for Aim 2

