Analyses for Aim 2 will include an analysis of variables collected utilizing tools adapted from the following validated scales: Avoidant Behaviors Scale (CESR, 2020), Contact Tracing Cooperation Scale, COVID-19 Household Environment Scale (Behar-Zusman, 2020), COVID-19 Family Impact Survey (The Center for Pediatric Traumatic Stress, 2020), COVID-19 Parent Relationships Scale (UCSD, 2020), and their relationships with key predictors (COVID-19 exposure), confounders (i.e. previous infection or vaccination) and moderators (i.e. age, gender, essential worker status). These scales capture variables such as reasons why participant was not tested, attitudes toward people who get tested, and workplace PPE accessibility. Variables included in the analysis for Aim 2 are nominal, ordinal, and discrete in nature. The initial analysis will summarize the variables of interest at the individual and household level for the baseline and follow-up timepoints. Nominal and ordinal variables will be summarized using frequencies and percentages. Bivariate analyses will be conducted to examine associations between the facilitators and barriers to COVID-19 precautions and key predictors (intervention group), confounders (e.g., previous infection, vaccination, moderators (e.g. gender, testing fatigue), and demographic characteristics (e.g., age, race, essential worker). To examine bivariate associations between continuous variables that are approximately normal or may become approximately normal after an appropriate transformation, the Student's t-test will be used. For other continuous variables where normality cannot be assumed, the Wilcoxon rank-sum test will be used instead. Chi-square tests will be used to assess group differences for nominal data. We will use Chi-square tests and the Cochran Mantel-Haenszel tests for comparison in ordinal characteristics (i.e. how often participant washes hands, uses PPE, agreeableness to isolate). The Fisher's exact test will be considered for contingency tables with sparse cells. We will compare outcomes across 3 racial/ethnic groups (White, Black, Hispanic). These differences will be examined in bivariate analyses (unadjusted) and multivariable analysis (adjusted). We will develop multilevel multivariable regression models to examine the association between predictors, mediators,

and moderators on COVID protection practices.

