Aim 4 is to (With our community advisors) develop, implement and test the effectiveness of a Nurse-Community Health Worker-Family Partnership intervention to increase reach, acceptance and uptake of diagnostic testing, adherence to COVID-19 prevention strategies, and development of a household mutual aid strategy to respond to COVID-19 related events within the home and community.

Analysis for Aim 4

The analysis for Aim 4 will encompass all variables of interest in Aims 1, 2, and 3 collected at baseline, six months, and nine months. Descriptive analyses will include participant and household level testing uptake, adherence to public health mitigation strategies, and household cohesion at each of the time points for the randomized controlled trial. Data will be stratified with respect to important demographic factors (e.g., age, race, gender, ethnicity). Continuous variables will be summarized using the mean, standard deviation, median, range, and interquartile range, while nominal and ordinal variables will be summarized using frequencies and percentages. Bivariate analyses will be conducted to examine associations between the outcomes of interest (testing uptake, COVID mitigation practices, and household mutual aid) and key predictors (intervention group), confounders (previous infection or vaccination), moderators (e.g., gender, age, testing fatigue), and demographic characteristics. To examine bivariate associations between continuous variables that are approximately normal or may become approximately normal after an appropriate transformation, the Student's t-test will be used. For other continuous variables where normality cannot be assumed, the Wilcoxon rank-sum test will be used instead. Chi-square tests will be used to assess group differences for nominal data. We will use Chi-square tests and the Cochran Mantel-Haenszel tests for comparison in ordinal characteristics. The Fisher's exact test will be considered for contingency tables with sparse cells. We will compare outcomes

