across 3 racial/ethnic groups (White, Black, Hispanic). These differences will be examined in bivariate analyses (unadjusted) and multivariable analysis (adjusted). We will develop multilevel multivariable regression models to examine the association between predictors, mediators, and moderators on the primary outcome (testing uptake) and secondary outcomes (COVID mitigation practices, and family mutual aid). We will use multivariable multilevel logistic (binary outcomes) and linear (continuous outcomes) regression models to conduct cross-sectional analysis at each time point. For outcomes where statistical distributional assumptions are violated we will use the *non-parametric multilevel mixture model (NPMM)*. In this model, latent classes are extracted at multiple levels of a hierarchical data structure (e.g., individual, household) and, unlike the conventional multilevel models (MLM), there are no continuously distributed random effects.^{1,2}

Longitudinal Analysis

We will use a random-intercepts logistic (with a binary response) or linear (continuous outcome) multilevel regression model, for each timepoint t , individual i , that is a member of household j . A random-intercepts model will give the conditional assessment of the extent to which household-level exposures vary on the outcomes after taking into account individual-level exposures, assuming the household-level variation is normally and independently distributed with a constant variance. The variance partitioning coefficient (VPC), or the amount of variability in the outcome attributed to predictors at each level, will be calculated. This will tell us to which extent household level and individual-level variables contribute to the outcome allowing for an examination of the impacts of COVID-19 at multiple levels. Structural equation models (SEM) will be used to examine mediating and moderating variables in the regression analyses. In addition, we will conduct sensitivity analyses (e.g., intent to treat vs receive intervention, components of intervention received, per protocol) and subgroup analyses (e.g., race/ethnicity, gender, age, education, essential worker) based on findings from aims 1-3.

For binary outcomes, we will use a random-intercepts logistic multilevel regression model, for each timepoint t , individual i , that is a member of household j . The basic equation will follow the form:

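### The SAP labels test frequency as nominal, so its comparison between arms would ignore the order of the categories, and no ordinal or count model is named for it

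*SAP*

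**What the plan says.** - **SAP, Analysis for Aim 1.** Test frequency is given as an example of a nominal variable: "Nominal variables (i.e. COVID-19 symptoms, test frequency) will be summarized using frequencies and percentages". The test for that data type follows: "Chi-square tests will be used to assess group differences for nominal data". The baseline comparison of arms has its own test: "A two-sample test for proportions will be used to compare the baseline testing practices of the two treatment groups".
- **SAP, Analysis for Aim 4.** The trial comparison inherits the earlier variables: "The analysis for Aim 4 will encompass all variables of interest in Aims 1, 2, and 3 collected at baseline, six months, and nine months". It examines associations with intervention group by data type: t-test or Wilcoxon for continuous variables, chi-square for nominal ones. For ordered ones: "We will use Chi-square tests and the Cochran Mantel-Haenszel tests for comparison in ordinal characteristics".
- **SAP, Analysis for Aim 2.** Behaviour frequency items are explicitly called ordinal: "comparison in ordinal characteristics (i.e. how often participant washes hands, uses PPE, agreeableness to isolate".
- **SAP, Analysis for Aim 4, regression models.** "We will use multivariable multilevel logistic (binary outcomes) and linear (continuous outcomes) regression models". No ordinal or count outcome model is listed. The longitudinal section also gives equations only for binary and continuous outcomes.

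**The concern.** How often someone has been tested is ordered: more tests is more testing. The SAP separates nominal from ordinal elsewhere, so the label has consequences. A variable called nominal gets chi-square, and neither the Wilcoxon test (continuous data) nor the Cochran-Mantel-Haenszel (CMH) test (ordinal data) is assigned to it.

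The intervention offers a monthly PCR test, with additional rapid tests when household risk rises, so a plausible effect is a one-directional shift towards more frequent testing. A Pearson chi-square test on k classes and two arms has k − 1 degrees of freedom and spreads its power over patterns that nobody expects. What is at stake is that a real increase in how often people test is more likely to be reported as no difference.

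**Working it through.** **1. The plan's own power figure, for reference.** Inputs from the SAP's Power and Sample Size section: 100 and 50 households, 2 people each, 3 time points, correlations at their upper bounds of 0.7 and 0.3, proportions 0.25 and 0.10, alpha 0.05.

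- Design effect = 1 + (3 − 1)(0.7) + 3(2 − 1)(0.3) = 3.3.
- Effective observations: 600/3.3 = 181.8 and 300/3.3 = 90.9.
- Pooled proportion 0.20. Standard error under the null = √[0.16(1/181.8 + 1/90.9)] = 0.0514; under the alternative = √(0.1875/181.8 + 0.09/90.9) = 0.0450.
- Power = Φ[(0.15 − 1.96 × 0.0514)/0.0450] = 86.4%. With 15% attrition it is 79.8%, or 80.5% at correlations of 0.69 and 0.29.

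The stated figure of more than 80% is therefore reproduced to within rounding of the inputs. It concerns a binary outcome, for which category order does not arise.

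**2. Cost of ignoring order, in general.** Suppose a one-degree-of-freedom ordered test has 80% power (noncentrality 7.85). With the same noncentrality spread over k − 1 degrees of freedom:

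| Categories | Chi-square power | Loss (points) |
|---|---|---|
| 3 | 70.9% | 9.1 |
| 4 | 64.5% | 15.5 |
| 5 | 59.5% | 20.5 |
| 6 | 55.5% | 24.5 |

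For five categories the loss falls to 16.0 points if the ordered test has 90% power, and to 11.3 at 95%.

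**3. Applied to test frequency at one time point.** Design effect = 1 + (2 − 1)(0.3) = 1.3. Effective sizes are 200/1.3 = 153.8 and 100/1.3 = 76.9, taken as 153 and 76. Assumptions not in the documents: counts are Poisson, with mean −ln(1 − proportion with any test), and the top class is open-ended. The 10% v 25% contrast is the SAP's. The other two keep its 0.15 difference at assumed higher control rates. Each scenario used 20,000 simulated trials, two-sided 0.05.

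Four classes (0, 1, 2, 3 or more):

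| Any testing, control v intervention | Chi-square | CMH mean-score | Wilcoxon |
|---|---|---|---|
| 10% v 25% | 62% | 83% | 82% |
| 40% v 55% | 47% | 70% | 67% |
| 60% v 75% | 72% | 86% | 85% |

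Type I error was about 0.04 to 0.05 for all three tests. With 15% attrition, the 10% v 25% row becomes about 53% for chi-square and 75% for the mean-score test.

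**4. Varying what the documents leave open.** Losses against the mean-score test over the same three contrasts:

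- three classes: about 8 to 15 points;
- four classes: about 14 to 23 points;
- five classes: about 21 to 31 points.

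**5. A different shape of effect.** Suppose the intervention changes only whether people test, with the same frequency mix among those tested. With four classes the loss is about 10 to 15 points at 10% v 25% and about 5 to 8 at 40% v 55%. At 60% v 75% there is no loss, and chi-square may be up to about 4 points better.

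**The case against.** The case for leaving the plan alone has four parts.

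- **The label may be a slip.** It stands in a sentence about summarising baseline data, and the baseline arm comparison uses a test of proportions. The Analysis for Aim 4 does not repeat the label, and the protocol's Statistical methods section treats a related count (household members tested) as continuous. This is fair, but it shows that the documents are inconsistent. Nothing in Aim 4 moves test frequency to another class, so an analyst who follows the text arrives at chi-square.
- **Other methods could use the order.** A linear multilevel model would do so if the variable were treated as continuous, and the SAP allows robust and non-parametric methods when assumptions fail. That is possible, but it is not assigned to a variable called nominal. The mixture-model fallback replaces the random-effects distribution and names no ordinal or count outcome model.
- **The mechanism weakens by nine months.** The intervention lasts five months, and the nine-month question covers the preceding three, after the monthly offers end. This stands: a shift in frequency is more plausible at six months.
- **The consequence is limited.** This also stands. The comparisons concerned are unadjusted, and test frequency is not among the items listed in the SAP's outcome definitions.

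A reader might infer that the 5-point behaviour items are also compared without regard to order. The documents do not support that: they are classed as ordinal and CMH is named. In the simulations its mean-score form stayed within about 2 points of Wilcoxon. What remains is ambiguity. The form of CMH is not stated (general association ignores order), nor is it said whether CMH or the parallel chi-square decides. The SAP's plan to examine scale items one by one appears under Aim 3 (transport, health care, drug use), so it does not show that mask use or hand washing is at risk.

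**Conclusion.** The point holds for test frequency. The SAP misclassifies an ordered quantity as nominal, carries it into the six- and nine-month comparisons by arm under a chi-square rule, and names no ordinal or count model.

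No single figure for the lost power can be given, because the documents do not state the response categories. Under a Poisson shift the range is about 8 to 31 points across three to five classes. It depends on the assumed effective sizes, control rates and distribution. It shrinks, and at high testing rates disappears, if only the decision to test at all changes.

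It would be wrong to conclude that the primary analysis or the sample size is weakened. The primary testing question is Yes/No, scale summary scores keep their order, and the stated power concerns a binary outcome. At baseline, power to compare randomised arms matters little. This is a modest defect, easily corrected, in unadjusted comparisons outside the primary outcome.

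**What to change.** 1. **SAP, Analysis for Aim 1:** move test frequency from the nominal examples to ordinal or count, and state its response categories or that the raw count is recorded.
2. **SAP, Analysis for Aim 4:** name one order-using comparison of test frequency between arms. Options are the CMH row-mean-score test with its scores fixed in advance, or a mixed model with a household random intercept: ordinal for grouped frequency, negative binomial for a raw count. Only the mixed model also allows for household membership.
3. **SAP, Analysis for Aim 4, regression models:** add ordinal and count to the outcome types.
4. **SAP, Analyses for Aims 2, 3 and 4 (secondary clarification):** for ordinal characteristics, name the mean-score form of CMH as the deciding test in place of the parallel Pearson chi-square. Keep chi-square or Fisher's exact test for truly nominal items such as symptoms or reasons.

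The cost is a few sentences and standard routines. The downside is small: an ordered analysis works best when the effect runs roughly in one direction, which can be checked from the category percentages by arm.

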and newly emerging waves of COVID-19. For example, a recent study showed college campuses across the US reduced the number of infection cases by 96% after imposing routine diagnostic tests of asymptomatic students [11]. Furthermore, early detection allows individuals to seek treatment before the illness progresses in severity and optimize their chances of survival. The importance of availability and uptake of testing for early detection of COVID-19 is particularly salient in the context of innovative antiviral medications (Sotrovimab, Nirmatrelvir-Ritonavir, Remdesivir, and Molnupiravir) that are currently available, and for which effectiveness appears higher early in the disease cycle [12]. According to Phase 2/3 results of the EPIC-HR study, the Nirmatrelvir-Ritonavir pill significantly decreased the risk of hospitalization or death by 89% for those who took the pill within the first few days of experiencing symptoms [12].

While the significance of COVID-19 testing is well-documented, existing barriers prevent communities who need it the most from receiving it. For instance, long wait-times, sparse testing locations, fear of contracting the virus at testing sites, and language barriers were among a few of the concerns voiced by these underserved communities [13]. Additionally, undocumented and/or uninsured individuals face more challenges when testing sites impose restrictions to receive free COVID-19 tests. This highlights the growing need for new approaches to expand testing availability for all, particularly in communities with elevated risk of exposure and susceptibility to COVID-19.

Throughout the COVID-19 pandemic, healthcare facilities helped increase testing rates by offering walk-in appointments, setting up drive-through sites, and sending out in-home testing kits [14]. While these strategies provide numerous options for individuals to get tested, it places the burden of seeking them out on the individual. Moreover, these options only accommodate those with their own means of transportation or those who can afford the high costs of at-home COVID-19 test kits. As a result, COVID-19 testing rates are disproportionately lower in underserved communities. Underserved communities that face structural barriers to COVID-19 testing tend to disproportionately make-up people of color. For instance, a study found that testing rates decreased as the percentage of ethnic-minority

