### **Assignment of interventions: allocation**

#### Sequence generation {16a}

The allocation sequence will be generated using a computer algorithm prior to the begin of study enrolment.

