## **Trial Status**

*Trials* guidance: Authors should report the protocol version number and date, the date recruitment began, and the approximate date when recruitment will be completed.

Protocol Version 1: \_\_\_\_\_

Recruitment Start Date: July 23rd, 2021

Current Status: Recruiting

Anticipated End Date: July 31, 2022

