A Nurse-Community Health Worker-Family Partnership Model: Addressing Uptake of COVID-19 Testing and Control Measures

Statistical Analysis Plan (SAP)

Unique Protocol ID: 3P30DA011041-23S1

Protocol Version: 1.1

NCT #: NCT04832919

Document Date: 07/12/22

Contributors:

[name] – Senior Biostatistician

[name] – Junior Research Scientist/Data Manager

STATISTICAL DESIGN AND POWER

Measures.

Definition of Primary Outcomes

Household COVID testing uptake at the 9-month follow up is one of the main primary outcomes of interest. The investigative team will document all medical services administered by nurses during home visits, as well as self-reported information regarding COVID-19 testing uptake by study participants in the treatment and control groups. Participants will be asked whether they have received COVID-19 testing in the past three months [Yes/No]. Additionally, variables collected via the COVID-19 Symptoms, Diagnoses, and Testing Scale are the primary outcomes. This questionnaire is adapted from the COVID-19 Cannabis Health Questionnaire (CCHQ) (Vidot et al, 2020) and will measure COVID-19 symptoms, diagnoses, and testing. At the 9-month follow up point, participants will be asked questions regarding whether they are currently sick with an illness that might be related to COVID-19, any symptoms the participant experienced in the past three months [Check All That Apply], and the result of the participant's last COVID-19 test [Positive/Negative].

Definition of Secondary Outcomes

For the randomized trial, data collected utilizing the following questionnaires are secondary outcomes:

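### No calendar-period term is prespecified, although the 9-month testing windows appear to be spread over about a year; adding one is a cheap precision gain, not a correction of bias

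*SAP*

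**What the plan says.** **Dates.** Protocol, Trial Status, gives "Recruitment Start Date: July 23 rd , 2021", "Current Status: Recruiting" and "Anticipated End Date: July 31, 2022".

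**Primary outcome.** SAP, Definition of Primary Outcomes, at the 9-month visit: "Participants will be asked whether they have received COVID-19 testing in the past three months [Yes/No". The window is therefore months 6 to 9 after each household's own baseline.

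**Model.** SAP, Longitudinal Analysis, begins: "We will use a random-intercepts logistic (with a binary response) or linear (continuous outcome) multilevel regression model, for each timepoint t". For binary outcomes it then specifies a "random-intercepts logistic multilevel regression model, for each timepoint t , individual i , that is a member of household j". The example covariates are COVID-19 exposure or infection (time-varying), demographics and comorbidities (individual), and a household plan (household). The SAP's named confounders are previous infection and vaccination. Nothing refers to calendar time.

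**Allocation.** Protocol, Sequence generation {16a}: "The allocation sequence will be generated using a computer algorithm prior to the begin of study enrolment". The SAP's Randomization section adds only that a predetermined algorithm is entered in REDCap. Neither document mentions blocking or stratification.

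**The concern.** Two participants who are both at month 9 may be reporting on quite different calendar periods. Testing in a given three months plausibly depends on how much infection is circulating and on the guidance in force. The 5-month intervention has ended before the month 6 to 9 window opens, so ambient conditions matter in both arms.

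In the model as written, any shared calendar effect goes into the household random intercept. That keeps the test approximately valid but has three costs:

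- The interval for the arm comparison is wider than it need be.
- With only 50 control households, one arm may by chance have more of its windows in a high-testing period.
- The planned variance partitioning coefficient will count calendar variation as household variation.

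Calendar period of enrolment is fixed before randomisation, so adjusting for it cannot introduce post-randomisation bias. The exposure and infection covariates are no substitute, because they are measured after randomisation and the intervention may change them.

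**Working it through.** **1. Calendar spread.** 23 July 2021 to 31 July 2022 is 373 days. Months 6 to 9 run from late January to late April 2022 for a household entering on the first day, and from late January to late April 2023 for one entering on the last.

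**2. The plan's own power figure.** Inputs (SAP, Power and Sample Size): 100 and 50 households, k = 2 people, m = 3 timepoints, 0.25 vs 0.10, correlations taken at their limits of 0.7 and 0.3, two-sided 0.05.

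- Design effect = 1 + (m − 1)(0.7) + m(k − 1)(0.3) = 1 + 1.4 + 0.9 = 3.3.
- Effective n = 600/3.3 = 181.8 and 300/3.3 = 90.9.
- Power = 86.4% (pooled variance) or 91.6% (unpooled). After 15% attrition it is 79.8% or 86.8%.

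The stated figure of more than 80% is reproduced, with little to spare after attrition under the pooled formula.

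**3. Chance imbalance under simple randomisation.** Let a share s of windows fall in a high-testing period. The SD of the between-arm difference in that share is √[s(1 − s)(1/100 + 1/50)]. With s = 0.5 (assumed) this is √(0.25 × 0.03) = 0.087, so the 95% range is ±0.17. Multiplying by the swing in testing probability gives the shift in the estimated arm difference:

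- swing 0.10: ±0.017
- swing 0.20: ±0.034
- swing 0.40: ±0.068

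The target difference is 0.15.

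**4. Added within-household correlation.** For two equally common levels this is (swing/2)²/[p(1 − p)].

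- p = 0.10, swing 0.10: 0.0025/0.09 = 0.028.
- p = 0.40, swing 0.40: 0.04/0.24 = 0.167.

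The planning limit for within-household correlation is 0.3.

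**5. Effect of a quarter-of-enrolment term.** Simulation with 3,000 trials per scenario: 150 households of two people, a 9-month binary outcome, within-household correlation about 0.3, even entry over four quarters alternating low and high, true difference 0.15, no attrition. Household means were regressed on arm with robust standard errors. The swings are assumptions.

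| Control mean | Swing (low to high) | Power without | Power with | Gain (points) |
|---|---|---|---|---|
| 0.10 | 0 | 85.5% | 85.1% | −0.4 |
| 0.10 | 0.10 (0.05 to 0.15) | 85.9% | 86.5% | +0.6 |
| 0.10 | 0.18 (0.01 to 0.19) | 83.5% | 87.1% | +3.6 |
| 0.30 | 0.30 (0.15 to 0.45) | 60.8% | 66.2% | +5.4 |
| 0.40 | 0.40 (0.20 to 0.60) | 55.3% | 66.5% | +11.2 |

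Across these scenarios the unadjusted estimate under simple randomisation averaged 0.149 to 0.151, and type I error was about 5 to 6% with or without the term. A more extreme case (0.40, swing 0.60) went from 50.0% to 79.1%; I do not rely on it.

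**6. Blocked allocation (blocks of six, 4:2).** At control 0.40 and swing 0.40 the SD of the estimate hardly moves (0.0619 to 0.0613), because blocking already balances dates. Power still rises from 56.4% to 67.2%. The unadjusted standard error ignores that balance and is too large, with type I error 2.9% unadjusted and 4.9% adjusted.

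**7. A second set of assumptions.** Here there is 15% loss, household SD 1 on the logit scale, odds ratio 2.5 and simple allocation.

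- Control rates 5/10/20/40% by quarter (mean 75/4 = 18.75%): 58.3% to 67.5%.
- Control rates 5/10/30/60% (mean 105/4 = 26.25%): 55.6% to 69.5%.
- Repeat runs of these two gave gains of about 6 to 15 points.
- Control rates averaging 0.10: 5/15/5/15% gave 58.5% to 60.6% (about +3 in a further run), and 5/7/11/17% gave 59.9% to 61.5%.
- Flat rates: 62.5% to 61.5%.

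**The case against.** - **This is not a validity error.** Correct. Concurrent randomisation protects the comparison and the household intercept absorbs shared calendar effects. A reader might infer that waves bias the arm effect; the design gives no basis for that, and the simulated estimates are centred on the true difference.
- **The documents do not say that uptake follows waves.** Correct. Protocol, Background and rationale {6a}, says that testing helps to mitigate local spikes "and newly emerging waves of COVID-19", which concerns what testing does, not what drives it. A reader might take it as a statement that uptake tracks waves, but the text does not go that far. The nearest support is indirect: the Discussion reports advice that close contacts be tested at once, and section {11b} expects messages to follow changing guidance. Variation over the year is plausible but assumed.
- **The end date is unlabelled.** Also correct. It stands beside the recruitment start date, under a guidance line asking when recruitment will finish, in a text that is still recruiting and cites sources accessed in January 2022. End of follow-up is unlikely, since nobody enrolled after October 2021 could reach month 9 by then. Even accrual over the year is a further assumption.
- **Chance imbalance presupposes simple randomisation.** It does, and small blocks would nearly remove it. The power gain survives for the reason shown in the blocked case.
- **The covariate lists are only examples, so a calendar term could still be added.** True, but a term chosen after the data are seen lacks the protection of prespecification.

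**Conclusion.** The plan leaves out a cheap, pre-randomisation predictor that may be strong. The consequence is lost precision and, without blocking, possible chance imbalance.

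At the plan's own control rate of 0.10 the gain from adjusting is about 0 to 4 power points. It is about 5 to 15 points only if control testing is commoner (roughly 0.2 to 0.4) and swings widely. A reader might take a double-figure gain as the expected benefit. The documents do not support that, because they give no wave sizes and plan on 0.10.

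The conclusion rests on three assumptions: 31 July 2022 is the end of recruitment, entry is roughly even over the year, and testing varied with calendar time. It is a low-cost improvement worth making, not a defect in the validity of the primary test.

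**What to change.** 1. In the primary 9-month model, prespecify calendar quarter of enrolment as a fixed effect.
2. In the longitudinal models, add calendar period derived from the scheduled visit date (enrolment date plus study month). The actual visit date can depart from schedule, since the SAP anticipates out-of-window assessments, and so is not strictly fixed before randomisation.
3. Tabulate enrolment quarter by arm.
4. State whether the allocation sequence was blocked and, if so, the block sizes.

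The cost is SAP wording and three parameters in the primary model. If testing did not vary, the power loss is about 1 point or less (85.5% to 85.1% and 62.5% to 61.5% in the flat scenarios). Enrolled households are entered in REDCap, so the dates should be available, although the documents do not list them as fields. A risk difference standardised over the enrolled calendar distribution would be a useful optional summary, but the fix does not depend on it.
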